Infection	ICD	T84.5, T84.6, T84.7, M86.02, M86.12, M86.22, M86.32, M86.42, M86.52, M86.62, M86.82, M86.92 (only during hospital stay)
	OPS	5-780.47, 5-780.57, 5-780.67, 5-780.77, 5-780.87, 5-780.97, 5-785.17, 5-785.57, 5-785.77, 5-800.24, 5-800.25, 5-800.34, 5-800.35, 5-800.a4, 5-800.a5, 5-800.b4, 5-800.b5, 5-810.14, 5-810.15, 5-810.74, 5-810.75, 5-810.84, 5-810.85, 5-850.h2, 5-850.j2, 5-892.37, 5-892.47, 5-896.27, 8-989, 8-989.0, 8-989.1, 8-989.2, 8-989.3, 8-989.4, 8-989.5, 8-989.6
Infection, resistant	ICD	U80-83 (only during hospital stay)
	OPS	8-987
Joint damage / cartilage damage	OPS	5-780.37, 5-784.57, 5-784.67, 5-800.84, 5-800.85, 5-810.44, 5-810.45, 5-812.04, 5-812.05, 5-812.34, 5-812.35, 5-812.94, 5-812.95, 5-812.a4, 5-812.a5, 5-812.e4, 5-812.e5, 5-812.f4, 5-812.f5, 5-812.g4, 5-812.g5, 5-812.h4, 5-812.h5, 5-812.k4, 5-812.k5, 5-812.m4, 5-812.m5
Luxation	OPS	8-201.4, 8-201.5 (also including outpatient sector after discharge)
Malunion	OPS	5-781.07, 5-781.17, 5-781.27, 5-781.37, 5-781.47, 5-781.57, 5-781.67, 5-781.77, 5-781.87, 5-781.97
Nerve injury	OPS	5-040.1, 5-040.2, 5-040.3, 5-041.1, 5-041.2, 5-041.3, 5-044.1, 5-044.2, 5-044.3, 5-045.1, 5-045.2, 5-045.3, 5-046.1, 5-046.2, 5-046.3, 5-047.1, 5-047.2, 5-047.3, 5-048.1, 5-048.2, 5-048.3, 5-049.1, 5-049.2, 5-049.3, 5-04b.1, 5-04b.2, 5-04b.3, 5-050.1, 5-050.2, 5-050.3, 5-051.1, 5-051.2, 5-051.3, 5-052.1, 5-052.2, 5-052.3, 5-053.1, 5-053.2, 5-053.3, 5-054.1, 5-054.2, 5-054.3, 5-055.1, 5-055.2, 5-055.3, 5-056.1, 5-056.2, 5-056.3, 5-057.1, 5-057.2, 5-057.3 (only during hospital stay)
Non-union / Pseudoarthrosis (if coded after six months)	OPS	5-781.a7, 5-782.17, 5-782.27, 5-782.37, 5-782.47, 5-782.57, 5-782.a7, 5-782.b7, 5-784.07, 5-784.17, 5-784.27, 5-784.37, 5-784.47, 5-784.77, 5-784.87, 5-784.b7
Osteonecrosis	ICD	M87.22, M87.32, M87.82, M87.92
Postoperative stiffness, Adhesive capsulitis, Frozen elbow	OPS	5-800.64, 5-800.65, 5-800.c4, 5-800.c5, 5-810.24, 5-810.25, 5-810.94, 5-810.95

Vascular injury	OPS	5-388.12, 5-395.12, 5-397.12 (only during hospital stay)

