Implant removal (TBW)	OPS	5-787.07, 5-787.17, 5-787.27, 5-787.67, 5-787.77, 5-787.g7, 5-810.34, 5-810.35
Revision of the osteosynthesis (LPF and TBW)	OPS	5-785.07, 5-785.17, 5-785.27, 5-785.37, 5-785.47, 5-785.57, 5-785.67, 5-785.77, 5-789.37, 5-78a.07, 5-78a.17, 5-78a.27, 5-78a.57, 5-78a.67, 5-78a.77, 5-78a.87, 5-78a.97, 5-78a.c7, 5-78a.g7, 5-78a.k7, 5-78a.m7, 5-78a.n7, 5-78a.x7, 5-793.07, 5-793.17, 5-793.27, 5-793.37, 5-793.67, 5-793.77, 5-793.87, 5-793.97, 5-793.a7, 5-793.b7, 5-793.c7, 5-793.g7, 5-793.h7,

		5-793.k7, 5-793.m7, 5-793.n7, 5-793.x7, 5-794.07 , 5-794.17, 5-794.27, 5-794.57, 5-794.67, 5-794.77, 5-794.87, 5-794.a7, 5-794.b7, 5-794.c7, 5-794.g7, 5-794.h7, 5-794.k7, 5-794.m7, 5-794.n7, 5-794.x7, 5-824.4 , 5-824.5, 5-825.01 , 5-825.4, 5-825.a, 5-825.m
Resection arthroplasty (for spacer placement)	OPS	5-829.4
Secondary arthroplasty	OPS	5-824.4 , 5-824.5
Arthrolysis	OPS	5-800.64 , 5-800.65, 5-810.24 , 5-810.25, 5-810.94, 5-810.95
Classification of complications and long-term endpoints/events		
Major adverse event		resuscitation, cardiac arrest, myocardial infarction, stroke, acute renal failure, acute liver failure, acute respiratory distress syndrome, sepsis or death from any case
Thromboembolic event		Deep vein thrombosis, pulmonary embolism, ischemic stroke or death from any case
Surgical complications		Adhesive capsulitis, arthrolysis, debridement, frozen elbow, implant removal within first 3 months, infection, infection with antibiotic-resistant germs, joint damage/cartilage damage, luxation, delayed union, non-union/pseudoarthrosis, malunion, nerve injury, vascular injury, osteonecrosis, postoperative stiffness, secondary arthroplasty, secondary arthroscopy, secondary surgery (open) including revision surgery, upper limb amputation
Implant-associated complications (IAC)		Impingement, bursitis, mechanical malfunction or material failure/loosening, periprosthetic or periimplant fracture
Non-implant associated complications (non-IAC)		Infection, infection with antibiotic-resistant germs, hematoma after surgery

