3.2.1. Primary Endpoints

Variable	Definition
Revision	
 - Time from surgery to revision defined above.
Implant removal (only)	
 - Time from surgery to implant removal - Within first 3 months after surgery, an implant removal will also be considered as a surgical complication - No SC is allowed to occur within 3 months and on the same day
Surgical complications (SC)	
 - Time from surgery of OF to surgical complications, with death being considered as a competing risk event.
In-hospital SC rate (IH-SC)	
 - SC after surgery during index hospitalization (yes/no)
In-hospital implant-associated complications (IH-IAC)	
 - IAC after surgery during index hospitalization
In-hospital non-implant associated complications (IH-non-IAC)	
 - Non-IAC after surgery during index hospitalization

Table 3: Primary endpoints

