3.3. Possible sources of bias due to variable definition

In-hospital complications will be defined by the above reported codes that are coded in the same inpatient case as the surgery of OF (i.e. the index case series). For all OPS codes, the date has to be later in course of hospitalization than the surgery of OF (datum surgery with LPF/TBW < datum OPS code). ICD codes are all coded at the date of discharge and no chronological order within one case will be available. However, the defined complications are of such a serious nature that they always represent an unfavorable scenario from the patient's point of view, irrespective of the chronological course during hospitalization. It can also be assumed that, preoperatively, they did not represent a contraindication for surgery, if they were present before. Thus, it can be firstly assumed that complications predominantly occurred after surgery and, secondly, that any bias from (a few) events happens before surgery should be very low. In summary, all ICD codes for the above-mentioned complications that will be coded during the index case will be considered as in-hospital complications.

For all SC, only OPS ipsilateral coded procedures will be considered as complications. For ICD codes, no laterality will be available and thus, SC during follow-up will be mostly defined on OPS codes. For

osteonecrosis, however, it is therefore possible to wrongly count contralateral events as a complication which might add some bias, but both groups will be effected in the same manner.

4. Statistical Methods

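### A resistant-germ code with no body site counts on its own as a surgical complication in the index stay, and for OPS 8-987 and 8-989 Table 2 conflicts with the ipsilateral rule

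*Combined protocol and SAP*

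**What the plan says.** Section 3.1, Table 2, has two infection rows among the surgical complications.

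- The resistant row contains ICD "U80-83 (only during hospital stay" and OPS 8-987, and nothing else.
- The general Infection row lists ICD codes, limited to the hospital stay, and OPS codes. The OPS list ends with "8-989, 8-989.0, 8-989.1, 8-989.2, 8-989.3, 8-989.4, 8-989.5, 8-989.6".

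Both rows feed two composites. The SC list includes "infection, infection with antibiotic-resistant germs, joint damage/cartilage damage". Non-IAC has only three components: "Infection, infection with antibiotic-resistant germs, hematoma after surgery".

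Three of the six primary endpoints in Table 3 (section 3.2.1) rest on these composites:

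- SC: "Time from surgery of OF to surgical complications, with death being considered as a competing risk event"
- IH-SC: "SC after surgery during index hospitalization (yes/no"
- IH-non-IAC: "Non-IAC after surgery during index hospitalization"

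Section 3.3 gives the counting rules. Any listed ICD code in the index case is taken as an in-hospital complication, because ICD codes have no order in time within a case. OPS codes must be dated after the index operation. On side, the rule is: "For all SC, only OPS ipsilateral coded procedures will be considered as complications". The section says that ICD codes carry no laterality, and it names osteonecrosis as the place where wrong-side events may be counted. It does not mention resistant infection or OPS codes without a side.

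**The concern.** Most codes in the Infection row point to the elbow region through a site character. The resistant-infection codes do not, and nothing ties them to an elbow infection. A resistant germ found elsewhere in the body during the index stay is then recorded as a complication of the fixation.

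Such events plausibly follow general health and time in hospital more than the choice of implant. Equal off-site coding in both arms pulls the TBW/LPF odds ratio towards 1. Unequal coding creates a difference where there is none. The aim of finding independent risk factors is also exposed, because sicker patients would appear to have more surgical complications. A falsely counted SC can further disqualify an event under Implant removal (only), since Table 3 does not allow that endpoint alongside an SC.

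For 8-987 and 8-989.x, two analysts could follow the plan faithfully and build different primary endpoints.

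**Working it through.** The plan states no event rate, effect size or sample size, so there is no figure of its own to reproduce. The check has three parts.

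**1. Which codes carry a site character (Table 2)?**

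| Row | Codes | With site character | Without |
|---|---|---|---|
| Infection, OPS | 36 | 28 (ending 7, 4, 5 or 2) | 8 (8-989, 8-989.0 to .6) |
| Infection, ICD | 12 | 9 (M86.x2) | 3 (T84.5, T84.6, T84.7) |
| Resistant, ICD and OPS | U80-83; 8-987 | none | all |

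The resistant row has no site-specific route at all. The absence of a site is read from the form of the codes; the documents do not print the classification texts.

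**2. Where does each code end up under section 3.3?**

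| Code | IH-SC | IH-non-IAC | SC after discharge |
|---|---|---|---|
| U80-83 | counts | counts | no, if hospital stay means the index stay |
| 8-987, 8-989.x | Table 2: yes; ipsilateral rule: no | Table 2: yes; the rule is worded for SC, so its reach is unclear | Table 2: yes; ipsilateral rule: no |

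An index-stay event in IH-SC is also an event in SC. Reading the hospital-stay limit as the index stay fits section 3.3, which says SC during follow-up rests mostly on OPS codes and names only osteonecrosis, an ICD entry without that limit, as the exception.

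**3. What could the size be?** All rates here are assumptions. Let p be the true elbow-infection risk and f the risk of an off-site code, independent and equal in both arms. The observed risk is q = 1 − (1 − p)(1 − f), and the observed OR is [q1/(1 − q1)] / [q0/(1 − q0)].

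Take p1 = 1% and p0 = 2%. For f = 2%:

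- q1 = 1 − 0.99 × 0.98 = 0.0298
- q0 = 1 − 0.98 × 0.98 = 0.0396
- OR = (0.0298/0.9702) / (0.0396/0.9604) = 0.745

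Sample size per arm uses the two-proportion formula (two-sided 5%, 80% power, pooled variance under the null, no continuity correction): n = [1.96·√(2q̄(1 − q̄)) + 0.842·√(q1(1 − q1) + q0(1 − q0))]² / (q1 − q0)², where q̄ is the mean of q1 and q0. Power is for an assumed 2,000 per arm and a single test before the Holm adjustment.

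| f per arm | OR | n per arm | Power, n = 2,000 | Off-site share, 2% arm |
|---|---|---|---|---|
| 0 | 0.495 | 2,319 | 74.0% | 0% |
| 0.25% | 0.550 | 2,706 | 67.3% | 10.9% |
| 0.5% | 0.594 | 3,096 | 61.5% | 19.7% |
| 1% | 0.661 | 3,881 | 52.0% | 32.9% |
| 2% | 0.745 | 5,474 | 39.5% | 49.5% |

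With true risks of 2% and 4% the effect is milder. The OR goes from 0.490 at f = 0 to 0.655 at f = 2%, and power at 2,000 per arm from 96.0% to 81.6%.

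If there is no true difference (2% in both arms) but off-site coding is 0.5% versus 1%, then q1 = 1 − 0.98 × 0.995 = 0.0249 and q0 = 1 − 0.98 × 0.99 = 0.0298, a spurious OR of 0.83.

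**The case against.** **A stronger reading that a reader might infer.** One could conclude that 8-987 and 8-989.x from any later, unrelated admission count as SC throughout follow-up. With assumed true SC risks of 15% versus 10% and 5% unrelated codes per arm, the risks become 1 − 0.85 × 0.95 = 19.25% and 1 − 0.90 × 0.95 = 14.5%, and the risk ratio falls from 1.50 to 1.33. The documents do not support this as a finding. The ipsilateral rule, read literally, excludes OPS codes without a side from SC, and U80-83 is limited to the hospital stay. The follow-up effect exists only if the rule is waived for these codes.

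**The case for leaving the definition alone.**

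- *Section 3.3 is open about ICD coding and argues that the events are serious whenever they occur.* True, but that argument concerns timing around surgery, not body site.
- *Both arms are affected alike after matching and adjustment.* Equal misclassification still pulls the odds ratio towards 1, although the absolute difference hardly moves (1.00 to 0.98 points at f = 2%). Equality is not assured either. The baseline Infection row omits U80-83 and 8-987, so earlier resistant-germ status is not matched. Section 4.2 itself prefers 30-day mortality to in-hospital death because length of stay may differ between arms, and codes collected over the index stay share that exposure. Unequal coding nevertheless remains a possibility, not something the documents show.
- *A sensitive definition is a legitimate choice in claims data.* This stands in part: requiring a linked code will miss some true elbow infections. But the plan does not present the choice as deliberate, and section 4.3 varies only the weights, never the endpoint definitions. IH-non-IAC is not in that sensitivity analysis at all.
- *The effect may be small.* This stands. At f = 0.25% the OR moves only from 0.495 to 0.550.

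**Conclusion.** The point holds for U80-83 on the plan's own text. A resistant-germ code from any body site in the index stay scores, without any elbow infection code, in IH-SC and IH-non-IAC, and in SC through that stay. Nothing in the matching or the planned sensitivity analyses corrects or reveals this.

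For 8-987 and 8-989.x the point is narrower: Table 2 and the ipsilateral rule contradict each other and must be reconciled.

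The size cannot be determined from the documents. The OR range of 0.55 to 0.75, against 0.495 with a site-specific definition, assumes true risks of 1% and 2%, independent off-site coding of 0.25% to 2%, and equal coding in both arms. It would be wrong to infer that most counted events are unrelated: that requires off-site coding to exceed the true rate, which nothing in the documents shows. The conclusion also rests on reading the missing site from code structure and on taking the hospital-stay limit to mean the index stay.

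The point deserves correction before analysis because it concerns primary endpoints in the Holm-adjusted family.

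**What to change.** 1. In Table 2, state that U80-83, 8-987 and 8-989.x do not qualify on their own for SC, IH-SC or IH-non-IAC. Use them only to label an event that already qualifies in the same case through another Infection-row code: an ipsilateral 5-xxx code dated after the index surgery or, in the index stay, M86.x2 or T84.5 to T84.7. Note that the T84 codes carry no site character either, so a link through them is weaker.
2. Report unlinked codes as a general complication.
3. In section 3.3, state that the ipsilateral rule excludes OPS codes without a side, and say that the same handling applies to IH-non-IAC.
4. Add a sensitivity analysis that counts the unlinked codes in SC, IH-SC and IH-non-IAC.

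A linked case already scores as Infection, so step 1 in effect removes these codes as stand-alone events; the text should say so. The cost is a few sentences, one condition in the code and one extra analysis. The downside is slightly fewer events, and a true resistant elbow infection with no local code is missed in the main analysis. Step 4 shows how much depends on that.

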Hormonal contraceptives for systemic use	ATC	G03A (only for matching)
General Complications		
Acute liver failure	ICD	K72.0, K72.7, K72.9
Acute myocardial infarction	ICD	I21, I22
Acute renal failure	ICD	N17
Acute respiratory distress syndrome	ICD	J80
Cardiac arrest	ICD	I46
Deep vein thrombosis	ICD	I80.1, I80.2, I82.2, I82.3
Delirium	ICD	F05
Pulmonary embolism	ICD	I26
Sepsis	ICD	A41, A40, B37.7, R65.0, R65.1, R65.9, R57.2
Stroke	ICD	I60-I64
Ischemic stroke	ICD	I63-I64
Resuscitation	OPS	8-77 (also defined as complication, if it happens on the same day as surgery)
Intensive care	OPS	8-980, 8-98f (only during hospital stay)
Blood transfusion	OPS	8-800.0, 8-800.1, 8-800.c (only during hospital stay)
Surgical complications (at least one day after surgery)		
Conversion to TBW	OPS	5-793.27, 5-794.17
Conversion to LPF	OPS	5-794.k7, 5-793.k7
Endoprosthetic joint and bone replacement	OPS	5-824.40, 5-824.41, 5-824.50, 5-824.51, 5-824.52
Conversion to other fracture fixation	OPS	5-790.07, 5-790.17, 5-790.27, 5-790.37, 5-790.47, 5-790.57, 5-790.67, 5-790.97, 5-790.d7, 5-790.k7, 5-790.m7, 5-790.n7, 5-790.p7, 5-790.x7, 5-793.17, 5-793.37, 5-793.67, 5-793.77, 5-793.87, 5-793.97, 5-793.a7, 5-793.b7, 5-793.c7, 5-793.g7, 5-793.h7, 5-793.m7, 5-793.n7, 5-793.x7, 5-794.07, 5-794.27, 5-794.57, 5-794.67, 5-794.77, 5-794.87, 5-794.a7, 5-794.b7, 5-794.c7, 5-794.g7, 5-794.m7, 5-794.n7, 5-794.x7
Conversion, any	OPS	Any conversion as defined above
Upper limb amputation, ipsilateral (exarticulation elbow or forearm)	OPS	5-862.2, 5-862.3, 5-862.4
Bursitis	ICD	M70.2, M70.3 (only during hospital stay)
Compartment syndrome	ICD	S51.86 (only during hospital stay)

Consequences of injury of the upper extremity	ICD	T92.1 (only during hospital stay)
Haematoma after surgery	ICD	T81.0 (only during hospital stay)
Implant dislocation	ICD	T84.11 (only during hospital stay)
Mechanical malfunction or material failure/loosening	ICD	T85.88, T85.9 (only during hospital stay)
Peri-prosthetic or peri-implant fracture	ICD	M96.6, T84.11 (only during hospital stay)
Surgical incidents	ICD	Y69, Y82.8, Y84.9 (only during hospital stay)
Delayed union (if coded within six months)	OPS	5-781.a7, 5-782.17, 5-782.27, 5-782.37, 5-782.47, 5-782.57, 5-782.a7, 5-782.b7, 5-782.x7, 5-784.07, 5-784.17, 5-784.27, 5-784.37, 5-784.47, 5-784.77, 5-784.87, 5-784.b7, 5-784.c7, 5-784.d7, 5-784.e7, 5-784.f7, 5-784.x7

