Secondary surgery, open (LPF and TBW)	OPS	5-780.07, 5-780.17, 5-780.27, 5-780.37, 5-780.67, 5-780.x7, 5-782.17, 5-782.27, 5-782.37, 5-782.47, 5-782.57, 5-782.a7, 5-784.07, 5-784.17, 5-784.27, 5-784.37, 5-784.47, 5-784.57, 5-784.67, 5-784.77, 5-784.87, 5-784.a7, 5-784.b7, 5-785.07, 5-785.17, 5-785.27, 5-785.37, 5-785.47, 5-785.57, 5-785.67, 5-785.77, 5-789.b7, 5-789.c7, 5-794.07, 5-794.27, 5-794.57, 5-794.67, 5-794.77, 5-794.87, 5-800.14, 5-800.15, 5-800.34, 5-800.35, 5-800.44, 5-800.45, 5-800.54, 5-800.55, 5-800.74, 5-800.75, 5-800.84, 5-800.85, 5-800.94, 5-800.95, 5-800.x4, 5-800.x5, 5-801.04, 5-801.05, 5-801.34, 5-801.35, 5-801.44, 5-801.45, 5-801.b4, 5-801.b5, 5-801.c4, 5-801.c5, 5-801.g4, 5-801.g5, 5-801.h4, 5-801.h5, 5-801.k4, 5-801.k5, 5-801.m4, 5-801.m5, 5-801.n4, 5-801.n5, 5-801.p4, 5-801.p5, 5-850.02, 5-850.12, 5-850.22, 5-850.32, 5-850.42, 5-850.52, 5-850.62, 5-850.72, 5-850.82, 5-850.92, 5-850.a2, 5-850.b2, 5-850.c2, 5-850.d2, 5-850.e2, 5-850.f2, 5-850.g2, 5-850.h2, 5-850.j2, 5-851.12, 5-851.22, 5-851.32, 5-851.42, 5-851.52, 5-851.62, 5-851.72, 5-851.82, 5-851.92, 5-851.a2, 5-851.b2, 5-851.c2, 5-851.d2, 5-852.02, 5-852.12, 5-852.22, 5-852.32, 5-852.42, 5-852.52, 5-852.62, 5-852.72, 5-852.82, 5-852.92, 5-852.a2, 5-852.b2, 5-852.c2, 5-852.d2, 5-852.h2, 5-852.j2, 5-853.02, 5-853.12, 5-853.22, 5-853.32, 5-853.42, 5-853.52, 5-853.62, 5-853.72, 5-853.82, 5-853.92, 5-853.x2, 5-855.02, 5-855.12, 5-855.22, 5-855.32, 5-855.42, 5-855.52, 5-855.62, 5-855.72, 5-855.82, 5-855.92, 5-855.a2, 5-855.b2, 5-859.02, 5-859.12, 5-862.2, 5-862.3, 5-862.4, 5-892.07, 5-892.17, 5-892.27, 5-892.37, 5-892.47, 5-896.07, 5-896.17, 5-896.27
Secondary arthroscopy (LPF and TBW)	OPS	5-782.b7, 5-784.c7, 5-784.d7, 5-784.e7, 5-784.f7, 5-810.04, 5-810.05, 5-810.14, 5-810.15, 5-810.24, 5-810.25, 5-810.44, 5-810.45, 5-810.54, 5-810.55, 5-810.64, 5-810.65, 5-810.74, 5-810.75, 5-810.84, 5-810.85, 5-810.94, 5-810.95, 5-810.x4, 5-810.x5, 5-811.24, 5-811.25, 5-811.34, 5-811.35, 5-811.44, 5-811.45, 5-811.x4, 5-811.x5, 5-812.04, 5-812.05, 5-812.34, 5-812.35, 5-812.94, 5-812.95, 5-812.a4, 5-812.a5, 5-812.e4, 5-812.e5, 5-812.f4, 5-812.f5, 5-812.g4, 5-812.g5, 5-812.h4, 5-812.h5, 5-812.k4, 5-812.k5, 5-812.m4, 5-812.m5, 5-812.x4, 5-812.x5, 5-819.04, 5-819.05, 5-819.14, 5-819.15, 5-819.x4, 5-819.x5
Implant removal (LPF)	OPS	5-787.07, 5-787.17, 5-787.37, 5-787.67, 5-787.77, 5-787.g7, 5-787.k7, 5-810.34, 5-810.35

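### The non-union code list omits six of the 22 delayed-union codes without explanation, and two of the six then appear in no other printed component row of the primary surgical-complications endpoint after six months

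*Combined protocol and SAP*

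**What the plan says.** Table 2 in section 3.1 has two rows for disturbed healing, each defined only by OPS codes and time of coding. One is labelled "Delayed union (if coded within six months"), the other "Non-union / Pseudoarthrosis (if coded after six months").

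Within the delayed-union row the 5-782 codes end and the 5-784 codes begin with "5-782.a7, 5-782.b7, 5-782.x7, 5-784.07", and the row closes with "5-784.b7, 5-784.c7, 5-784.d7, 5-784.e7, 5-784.f7, 5-784.x7". The corresponding stretch of the non-union row, to its end, is "5-782.a7, 5-782.b7, 5-784.07, 5-784.17, 5-784.27, 5-784.37, 5-784.47, 5-784.77, 5-784.87, 5-784.b7".

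The SC composite, defined later in Table 2, includes both rows: "delayed union, non-union/pseudoarthrosis, malunion, nerve injury". It also includes "secondary arthroscopy, secondary surgery (open) including revision surgery, upper limb amputation". The secondary-arthroscopy row has no time limit and begins "5-782.b7, 5-784.c7, 5-784.d7, 5-784.e7, 5-784.f7, 5-810.04".

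Table 3 lists time to SC as a primary endpoint with death as a competing risk. Section 4.2 plans cumulative incidences at 1 month, 3 months and 1 to 5 years.

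**The concern.** Where two rows share a code list and differ only by a six-month cut, a reader expects timing alone to decide the class. Here the list also shortens at the cut. A programmer who follows Table 2 literally will treat the same inpatient procedure differently on the two sides of six months, for no stated reason.

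Two things are at stake. The first is the definition of a primary endpoint: a procedure that counts towards SC at five months may not count at seven. All the planned SC time points from one year onwards lie beyond the cut. The second is the component labels: if delayed union and non-union are ever tabulated, they would rest on different code sets and could not be compared or added.

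**Working it through.** No sample size, power or alpha figure is involved. The check is a comparison of the printed lists.

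**Step 1. Count the codes.**

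| Code family | Delayed union (within six months) | Non-union (after six months) | Omitted from non-union |
|---|---|---|---|
| 5-781 | 1 (.a7) | 1 (.a7) | none |
| 5-782 | 8 (.17, .27, .37, .47, .57, .a7, .b7, .x7) | 7 | .x7 |
| 5-784 | 13 (.07, .17, .27, .37, .47, .77, .87, .b7, .c7, .d7, .e7, .f7, .x7) | 8 | .c7, .d7, .e7, .f7, .x7 |
| Total | 1 + 8 + 13 = 22 | 1 + 7 + 8 = 16 | 22 − 16 = 6 |

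No non-union code is absent from delayed union. The omitted share of codes is 6/22 = 27%.

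**Step 2. Rule out a text-extraction fault.** The non-union row passes from 5-782.b7 straight to 5-784.07, so 5-782.x7 is missing from the middle of the list. The row then ends at 5-784.b7 and the osteonecrosis row follows. A row cut off at its end would not explain the gap in the middle.

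**Step 3. Look up each omitted code in the other printed inpatient complication rows** (open secondary surgery, secondary arthroscopy, revision, malunion, joint damage, infection and the rest).

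| Code | Within six months | After six months |
|---|---|---|
| 5-784.c7, .d7, .e7, .f7 | SC, as delayed union and as secondary arthroscopy | SC, as secondary arthroscopy only |
| 5-782.x7, 5-784.x7 | SC, as delayed union only | in no printed SC component row |

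So four codes change label and two lose their only printed route into SC (2/22 = 9% of the delayed-union codes).

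**Step 4. Test whether overlap with other rows could explain the omissions.** Of the 16 retained non-union codes, 14 are also in open secondary surgery (six 5-782 codes and eight 5-784 codes) and one, 5-782.b7, is also in secondary arthroscopy: 14 + 1 = 15 of 16 overlap another row. Overlap was therefore not a ground for leaving a code out of non-union. Nor does it explain the two .x7 codes, which overlap nothing.

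**Step 5. When does SC change for a patient?** Only if 5-782.x7 or 5-784.x7 is coded as an inpatient procedure after six months and no other SC code came earlier or on the same date. If another SC code follows, the event is recorded late; if none follows, it is missed. In-hospital SC could be affected only if the index stay exceeded six months.

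**The case against.** The strongest reply is that nothing in the plan says the two lists must match. A narrower non-union definition could be deliberate: two of the omitted codes are residual .x codes that might be thought too unspecific, and the other four are arthroscopic codes already captured elsewhere. That identical lists were intended is indeed an inference. The plan's own pattern supports it, though: delayed union keeps both .x codes, and 5-782.b7 stays in non-union although it too is listed under arthroscopy. A deliberate difference would need a sentence of explanation, and there is none.

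A second reply concerns consequence, and most of it stands. Delayed union and non-union are not endpoints in Table 3 or Table 4; they enter the planned analyses as components of SC. Four of the six codes leave SC unchanged.

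Third, the SC composite names debridement, which has no code row of its own in Table 2. One therefore cannot exclude that its codes include one of the two .x7 codes. The defensible statement is that these two appear in no other printed SC component row.

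A reader might go further and infer that about a quarter of non-union events are lost, or that a reported non-union rate will be wrong. The 27% is a share of codes, not of events, and no separate non-union rate is a planned endpoint. A reader might also infer an artificial step in the SC hazard at six months. At most two residual codes in a composite with a very large number of codes could produce one, so it would be negligible. Nor do the documents support a claim of biased treatment comparison: the same lists apply to both arms, and nothing suggests that late use of these two codes differs between them.

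**Conclusion.** The point holds as an unexplained inconsistency in the definition of a primary-endpoint component. Six of 22 codes are missing from the non-union row. Four change only their component label after six months; two, 5-782.x7 and 5-784.x7, stop counting towards SC as far as the printed rows show.

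The effect on the SC results is likely to be small and the rule is common to both arms. It cannot be put into numbers because the documents give no code frequencies. Two assumptions carry the conclusion: that the rows were meant as one list split by time, and that the unlisted debridement codes do not include the two .x7 codes. This is a minor correction worth making because it is so easily made, not a threat to the study's conclusions.

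**What to change.** Before analysis, define both rows by one code list and let only the time window differ. Adding 5-782.x7 and 5-784.c7, .d7, .e7, .f7 and .x7 to non-union gives 16 + 6 = 22 codes in each row and keeps late events in SC. If the shorter list was intended, either apply its 16 codes to both windows or add a sentence saying why the windows differ. In the same edit, state which row takes a code dated exactly at six months, and print the codes meant by debridement.

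The cost is one table row and the matching lines in the code lists. No new data are needed.

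### Fourteen of the 50 conversion codes in Table 2 (all 5-790.x7), and resection arthroplasty (5-829.4), count in neither primary endpoint Revision nor SC, and no reason is given

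*Combined protocol and SAP*

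**What the plan says.** Section 3.1, Table 2, has a block of surgical complications counted from at least one day after surgery. It contains rows for conversion to TBW, to LPF, to joint replacement, and "Conversion to other fracture fixation". The last of these begins with the codes "5-790.07, 5-790.17, 5-790.27, 5-790.37, 5-790.47, 5-790.57, 5-790.67, 5-790.97, 5-790.d7, 5-790.k7, 5-790.m7, 5-790.n7, 5-790.p7, 5-790.x7" and continues with codes from 5-793 and 5-794. A further row, 'Conversion, any', is the union of these four. Later rows of the table give code lists for open secondary surgery, secondary arthroscopy, implant removal, revision of the osteosynthesis, and resection arthroplasty for spacer placement (5-829.4).

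A separate block at the end of Table 2 then classifies events into composites. The SC composite names its components one by one and closes with "secondary arthroplasty, secondary arthroscopy, secondary surgery (open) including revision surgery, upper limb amputation". It names neither conversion nor resection arthroplasty.

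Section 3.2.1 makes Revision a primary endpoint, defined as "Time from surgery to revision defined above", which points to the revision row of Table 2. SC, in-hospital SC and 'Implant removal (only)' are also primary. The last of these does not allow an SC on the same day. Section 3.3 explains that follow-up SC rests mostly on OPS codes because ICD codes carry no side.

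**The concern.** The plan labels 5-790, 5-793 and 5-794 procedures alike as conversions to another fixation. It then counts every listed 5-793/5-794 conversion as a revision, and no 5-790 conversion. Nothing in the text explains the difference, and the row for any conversion is defined but then used in no endpoint.

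Two primary endpoints are directly affected, Revision and SC. In-hospital SC is affected too when the procedure falls in the index stay. A fourth is exposed through its exclusion rule: if an implant is removed after month 3 and a 5-790 conversion is coded on the same day, the conversion is not an SC and so does not disqualify the removal. The event could then be recorded as implant removal only. Under Section 4.2 the treatment-effect p-values of all primary endpoints enter one Bonferroni-Holm family. The sensitivity analyses in Section 4.3 change the weights but not the event definitions, so they would not reveal the omission.

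**Working it through.** There is no stated figure to reproduce. The check is a comparison of code lists, all taken from Section 3.1, Table 2. A parent code such as 5-824.4 is taken to cover its sub-codes.

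**Step 1: size of the conversion set.** TBW 2, LPF 2, joint replacement 5, other fixation 41 (14 in 5-790, 14 in 5-793, 13 in 5-794). Total 2 + 2 + 5 + 41 = 50.

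**Step 2: conversion codes found in the Revision row.**

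| Conversion to | Codes | In Revision row | Missing |
|---|---|---|---|
| TBW | 2 | 2 | 0 |
| LPF | 2 | 2 | 0 |
| Joint replacement | 5 | 5 | 0 |
| Other fixation | 41 | 27 | 14 |
| Any | 50 | 36 | 14 |

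36/50 = 72% are covered and 14/50 = 28% are not. Within the other-fixation row, 14/41 = 34% are not. The missing codes are exactly the 5-790 group: .07, .17, .27, .37, .47, .57, .67, .97, .d7, .k7, .m7, .n7, .p7 and .x7.

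**Step 3: the SC composite, read in two ways.**

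- *Revision surgery means the full Revision row.* SC then contains the 36 codes above. No 5-790 code stands in any other component, including open secondary surgery, secondary arthroscopy, secondary arthroplasty, infection, delayed union, non-union, malunion, joint damage and implant removal. SC misses the same 14 of 50.
- *Revision surgery only describes the open-surgery row.* SC then catches six conversion codes through that row (5-794.07, .27, .57, .67, .77 and .87) and five joint-replacement codes through secondary arthroplasty, 6 + 5 = 11. It misses 50 − 11 = 39 of 50 (78%), including all four conversions to TBW or LPF.

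**Step 4: resection arthroplasty.** 5-829.4 is not in the Revision row, not in the open-surgery row and not in any other SC component. It is outside both endpoints on either reading.

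**Step 5: do the other composites pick these codes up?** The implant-associated and non-implant-associated composites name no conversion and no resection arthroplasty, so they do not.

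**Step 6: is there a stated reason?** The laterality argument in Section 3.3 concerns ICD codes. The codes at issue are OPS codes, and the same section relies on ipsilateral OPS coding. It therefore cannot account for the omission.

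**The case against.** The strongest reply is that the gap is narrow. Most conversions are counted: every conversion to TBW, LPF or joint replacement and all 27 of the 5-793/5-794 conversions are in the Revision row. Some of the codes also reach SC by a second route, through open secondary surgery or secondary arthroplasty. This stands, and it limits the point to 14 conversion codes and 5-829.4.

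A second reply is that events are counted per patient, not per code. Someone with a 5-790 or 5-829.4 procedure still counts in SC if another SC code is present, for example implant removal within three months, infection coded during a hospital stay, or open secondary surgery. This also stands for SC. It helps less for Revision, which needs a code from the Revision row itself: early implant removal or an infection diagnosis, for instance, is an SC but not a Revision.

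A third reply is that Table 2 lists variables and a separate block defines composites, so a listed variable need not enter one. That is a fair defence of the unassigned ICD rows. A reader might infer that these too are events lost by mistake. The documents do not support that: Section 3.3 gives a reason for limiting ICD codes in follow-up SC, and several of the ICD events are placed in the implant-associated or non-implant-associated composites for the index stay. The defence is weaker for the OPS codes, because most of the same conversion row is counted as revision and the rest is left out without comment.

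**Conclusion.** The point holds as a gap in the code lists. As written, 14 of 50 conversion codes and 5-829.4 count in neither Revision nor SC. A patient whose only later coded event is one of these is event-free for both, and for in-hospital SC if it occurs in the index stay. A removal on the same day after month 3 could be classed as implant removal only. Separately, the wording of the SC composite allows 14 or 39 of the 50 conversion codes to be missed, and the plan does not say which reading applies.

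Two stronger conclusions are tempting but not supported. One is that failed fixations in general go uncounted; 36 of 50 conversion codes are in Revision. The other is that the comparison of TBW with LPF is biased. That would require these codes to be used at different rates in the two arms, and the documents give no code frequencies. A share of codes is not a share of events, so neither the number of events lost nor the direction of any bias can be derived.

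The result assumes that the Table 2 lists are the operative definitions and that a parent code covers its sub-codes.

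**What to change.** 1. Add the 14 codes 5-790.x7 listed in the other-fixation row, and 5-829.4, to the Revision row.
2. Name 'Conversion, any' and resection arthroplasty in the SC composite.
3. State that revision surgery in the SC composite means the full Revision row.

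Conversion-code coverage then rises from 36/50 to 50/50 in Revision, and to 50/50 in SC whichever reading was meant. The existing rules on side and on dating after the index surgery would apply unchanged to the added codes. If any of these codes are left out on purpose, the plan should say so and give the reason.

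The cost is a small edit to Table 2 and the programmed code list, and a slightly broader event definition. No new data are needed.
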